- For UNCOMMON MUTATION COHORT, it will be defined according to the fields **[First-line treatment period / MUT1. MUT1_unc, MUT1_unc_ex20_sp, MUT1_unc_sp]**.
- For SEQUENCING COHORT, it will be defined according to the field **[First-line treatment period / MUT1. MUT1_seq]**.

EGFR mutational status at second-line treatment start

It will be defined according to the following fields recorded in the MUTATIONS form of the [**Second-line treatment period**] time period (when applicable); for UNCOMMON MUTATION COHORT, only patients with Number of NSCLC treatment lines (as defined before) >1 should be considered:

- if “Was mutational status re-evaluated at start of second-line treatment?” [**MUT2. MUT2_reeval**] = “No” OR if “Any changes in EGFR mutations at start of second-line treatment with respect to start of first-line treatment?” [**MUT2. MUT2_changes**] = “UNK”, patients will be classified as “Unknown EGFR mutational status”
- if “Any changes in EGFR mutations at start of second-line treatment with respect to start of first-line treatment?” [**MUT2. MUT2_changes**] = “No”, then the patient’s EGFR mutational status at second-line treatment start will be imputed as the same patient’s EGFR mutational status at first-line treatment start (as defined before)
- if “Any changes in EGFR mutations at start of second-line treatment with respect to start of first-line treatment?” [**MUT2. MUT2_changes**] = “Yes”, then the patient’s EGFR mutational status at second-line treatment start will be retrieved from the fields [**MUT2. MUT2_mut_start**, **MUT2_mut_start_ex20_sp**, **MUT2_mut_start_sp**, **MUT2_concom_mut_start**]

Acquired EGFR mutations at second-line treatment start

For both cohorts, the mutations found at start of second-line treatment (i.e. the options selected in the field [**MUT2. MUT2_mut_start**]) will be compared to the mutations found at start of first-line treatment (i.e. the options selected in the field [**MUT1. MUT1_mut_unc**] for the UNCOMMON MUTATION COHORT, or in the field [**MUT1. MUT1_mut_seq**] for the SEQUENCING COHORT). The mutations found at start of second-line treatment that were not present at first-line treatment start will be classified as acquired EGFR mutations.

EGFR mutational status at second-line treatment stop/end of observation

It will be defined according to the following fields recorded in the MUTATIONS form of the [**Second-line treatment period**] time period (when applicable):

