- if “Was mutational status re-evaluated at at stop of second-line treatment (or within end of observation, in case second-line treatment was not discontinued)?” [**MUT2. MUT2_reeval_stop**] = “No” OR if “Any changes in EGFR mutations with respect to start of second-line treatment?” [**MUT2. MUT2_changes_stop**] = “UNK”, patients will be classified as “Unknown EGFR mutational status”
- if “Any changes in EGFR mutations with respect to start of second-line treatment?” [**MUT2. MUT2_changes_stop**] = “No”, then the patient’s EGFR mutational status at second-line treatment stop/end of observation will be imputed as the same patient’s EGFR mutational status at second-line treatment start (as defined before)
- if “Any changes in EGFR mutations with respect to start of second-line treatment?” [**MUT2. MUT2_changes_stop**] = “Yes”, then the patient’s EGFR mutational status at second-line treatment stop/end of observation will be retrieved from the fields [**MUT2. MUT2_mut_stop**, **MUT2_mut_stop_ex20_sp**, **MUT2_mut_stop_sp**, **MUT2_concom_mut_stop**]

Acquired EGFR mutations at second-line treatment stop/end of observation

For both cohorts, the mutations found at stop of second-line treatment/end of observation (i.e. the options selected in the field [**MUT2. MUT2_mut_stop**]) will be compared to the mutations found at start of second-line treatment (i.e. the options selected in the field [**MUT2. MUT2_mut_start**]). The mutations found at second-line treatment stop/end of observation that were not present at start of second-line treatment will be classified as acquired EGFR mutations.

Classification of EGFR uncommon mutations (according to Yang's classification) for exploratory analyses

According to the MUTATIONS form, considering the EGFR mutational status at first- and second-line treatment start (but considering only lines containing EGFR-TKIs), the following definitions will be applied to classify patients' mutational status with respect to EGFR gene:

- **T790M-positive:** patients having T790M at start of either first- or second-line EGFR-TKI, but excluding patients developing acquired T790M at second-line osimertinib start;
- **Exon 20 insertion-positive:** patients having any type of exon 20 insertion at start of either first- or second-line EGFR-TKI, excluding patients included in group "a");

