- absolute and relative frequency of “Methodology used for mutation testing”, with details of ARMS, sequencing, NGS (according to the fields [*Second-line treatment period / MUT2. MUT2_meth_start, MUT2_meth_start_sp, MUT2_meth_ARMS, MUT2_meth_ARMS_sp, MUT2_meth_seq, MUT2_meth_seq_sp, MUT2_meth_NGS, MUT2_meth_NGS_sp*])

Descriptives and percentages will be calculated over the number of ELIGIBLE PATIENTS in the cohort, considering only patients with Number of NSCLC treatment lines >1 (see “Computed variables” chapter) with “Was mutational status re-evaluated at start of second-line treatment” [*Second-line treatment period / MUT2. MUT2_reeval*] = “Yes”.

[figure not shown]

Table 15-UNC. Mutations at second-line treatment stop/end of observation (ELIGIBLE PATIENTS of the Uncommon Mutation Cohort)

The table will provide:

- absolute and relative frequency of patients according to EGFR mutational status at second-line treatment stop/end of observation (see “Computed variables” chapter);
- absolute and relative frequency of patients according to Classification of EGFR uncommon mutations at second-line treatment stop/end of observation (see “Computed variables” chapter);
- absolute and relative frequency of patients according to acquired EGFR mutations at second-line treatment stop/end of observation (see “Computed variables” chapter);
- absolute and relative frequency of patients according presence/absence of other mutated genes and detail of mutations at second-line treatment stop/end of observation (according to the fields [*Second-line treatment period / MUT2. MUT2_oth_gene_stop_YN* (*), *MUT2_oth_gene_stop, MUT2_oth_gene_stop_sp*]).

(*) in case [*MUT2_oth_gene_stop_YN*] = “No”, then the patient’s mutational status for other genes at second-line treatment stop/end of observation will be imputed as the same patient’s mutational status for other genes at second-line treatment start.

Descriptives and percentages will be calculated over the number of ELIGIBLE PATIENTS in the cohort, considering only patients with Number of NSCLC treatment lines >1 (see “Computed variables” chapter) with “Was mutational status re-evaluated at stop of second-line treatment [...]” [*Second-line treatment period / MUT2. MUT2_reeval_stop*] = “Yes”.

Table 16-UNC. Approaches for detection of mutations at second-line treatment stop/end of observation (ELIGIBLE PATIENTS of the Uncommon Mutation Cohort) – Secondary objective #3

The table will provide:

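### Acquired EGFR mutations at second-line stop are derived against a raw eCRF field that may be blank, so original mutations can be tabulated as acquired in Table 15-UNC

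*SAP*

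**What the plan says.** Three derivations in SAP section 3 bear on this point.

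- **Status at second-line start.** If mutational status was not re-evaluated, or the change question is UNK, "patients will be classified as “Unknown EGFR mutational status". If the answer is No, the status "will be imputed as the same patient’s EGFR mutational status at first-line treatment start". Only if it is Yes does the rule go to the second-line form: "EGFR mutational status at second-line treatment start will be retrieved from the fields", of which MUT2_mut_start is the first.
- **Status at second-line stop or end of observation.** The same three branches apply, with change now judged against second-line start. Where a change is recorded, "EGFR mutational status at second-line treatment stop/end of observation will be retrieved from the fields", of which MUT2_mut_stop is the first.
- **Acquired mutations at stop.** The options in MUT2_mut_stop "will be compared to the mutations found at start of second-line treatment (i.e. the options selected in the field", and the field given is MUT2_mut_start. The rule then says: "The mutations found at second-line treatment stop/end of observation that were not present at start of second-line treatment will be classified as acquired EGFR mutations".

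SAP section 4.1.3 puts the result in Table 15-UNC as "absolute and relative frequency of patients according to acquired EGFR mutations at second-line treatment stop/end of observation". That table covers eligible patients with more than one treatment line who were re-evaluated at stop. It does not require re-evaluation at second-line start. Table 13-SEQ refers to the same specification.

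**The concern.** The rule for acquired mutations uses a raw field that the status rule treats as the source in only one of its three branches. In the other two, the status comes from first line or is declared Unknown, so the raw field probably holds nothing. By contrast, when a change is recorded at stop, MUT2_mut_stop supplies the whole status at stop, and the original mutations belong in it. Subtracting an empty list from a full one labels every listed mutation as acquired.

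At stake is the meaning of one descriptive item. Table 15-UNC would show driver mutations present before any treatment as if they had emerged by the end of second line, and a reader would take them for resistance mutations.

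**Working it through.** The documents give no figure to reproduce, so the check applies the rules as written.

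**Inputs.** Each time point has four possible states: re-tested with change Yes, re-tested with change No, re-tested with change UNK, and not re-tested. That gives 4 × 4 = 16 start-by-stop combinations. Table 15-UNC admits the three re-tested states at stop, so 4 × 3 = 12 of the 16 are in its denominator.

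**Assumption.** MUT2_mut_start is empty unless a change was recorded at second-line start, and MUT2_mut_stop is empty unless a change was recorded at stop. This follows the branching of the status rules; the eCRF itself is not available.

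**Rules compared.**
- As written: acquired = MUT2_mut_stop minus MUT2_mut_start.
- Alternative: acquired = computed status at stop minus computed status at second-line start.

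**Example.** The patient has G719X at first line and one further mutation, N, new at stop. In the first row the patient had also gained T790M by second-line start. All rows have change = Yes at stop.

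| State at second-line start | Raw start field | Computed start status | Stop field | Acquired, as written | Acquired, computed status |
|---|---|---|---|---|---|
| Change Yes | G719X, T790M | G719X, T790M | G719X, T790M, N | N | N |
| Change No | empty | G719X (carried forward) | G719X, N | G719X, N | N |
| Change UNK | empty | Unknown | G719X, N | G719X, N | undetermined |
| Not re-tested | empty | Unknown | G719X, N | G719X, N | undetermined |

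The rule as written counts the original mutation as acquired in the last three rows. In the other 16 − 3 = 13 combinations it does not: either the start field is filled or the stop field is empty. All three affected combinations lie within the 12 that Table 15-UNC admits.

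The clean case is the second row with N = T790M. The SAP itself regards G719X as present at second-line start, yet the rule reports two acquired mutations where one is right.

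**Sequencing cohort.** Criterion 6 in SAP section 2.1 requires MUT2_mut_start to include T790M. The field is therefore never blank in an eligible patient, and the mechanism does not arise in Table 13-SEQ.

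**Contrast within the SAP.** The classification of uncommon mutations at second-line start uses the computed status and is limited to patients with MUT2_reeval = Yes. For other genes, Table 15-UNC carries the second-line-start status forward when the answer at stop is No. The acquired-EGFR rule has neither provision.

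**The case against.** Five points can be made for the plan.

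1. **The substance of the rule is right.** Its closing sentence speaks of mutations not present at second-line start, and a careful programmer would not call a carried-forward G719X acquired. Field names in these paragraphs are also loose: the parallel rule at second-line start cites MUT1_mut_unc and MUT1_mut_seq, where the status rule uses MUT1_unc and MUT1_seq. This is a fair reading, but the rule names the raw field explicitly. Two readings with different output should not be left to the programmer.
2. **The eCRF is not visible.** If version 1.5.3 pre-fills MUT2_mut_start, or sites complete it after answering No, the error does not occur. This stands, and the point is conditional on it.
3. **Section 4 excludes patients with missing data from the analysis of a variable.** That might be read as dropping patients with a blank start field. But it is not tied to this variable, and criterion 10 in section 2.1 has a condition for mutation fields with no options selected. It would also remove no-change patients, whose status the SAP treats as known.
4. **A patient not tested at second-line start has no reference for the change question at stop.** UNK is a natural answer there, and it makes the stop status Unknown. This stands: the not-re-tested route needs a site to answer Yes regardless, which is why the no-change patient is the better illustration.
5. **Section 6 plans a plausibility and consistency review of all tables.** It does, but Table 15-UNC is not among those to be reprogrammed or independently verified, whereas Table 12-UNC is.

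A reader might infer that every patient re-tested at stop who was unchanged or untested at second-line start is misclassified. The documents do not support that. A change must also be recorded at stop, and the original mutation must still be listed there.

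**Conclusion.** The point holds as a conditional specification error of minor weight. Applied literally, the rule can count original mutations as acquired in Table 15-UNC. This requires an uncommon-cohort patient with no change, UNK or no re-test at second-line start, change = Yes at stop, and the original mutation listed at stop. It also requires MUT2_mut_start to be blank, which is inferred from the status rule.

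For each such patient, every original mutation still listed is wrongly added or, where second-line-start status is Unknown, added without a valid reference. How many patients this concerns cannot be derived, because the documents give no re-test rates.

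A reader might also suspect the main results. Nothing supports that: the time-on-treatment and overall survival derivations do not use this variable. Protocol section 9.7 asks for resistance mutations at osimertinib discontinuation in the sequencing cohort, where the start field cannot be blank.

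**What to change.** In SAP section 3, define acquired EGFR mutations at second-line stop or end of observation as the computed EGFR mutational status at that time minus the computed EGFR mutational status at second-line start, including the carry-forward from first line. Report patients whose second-line-start status is Unknown as not evaluable for this item, and show their number in Table 15-UNC. The same label is needed where the stop status is Unknown, since the difference is then undefined.

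Comparing Unknown patients with first-line status is not recommended for this table, because it would mix mutations acquired on either line.

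The cost is a short SAP wording change, a small change to the derivation and one extra table row. No new data are needed, and the definition is safe whether or not the eCRF pre-fills the field.

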- “4. Informed and privacy consent signature obtained depending on local regulations” in the ELIGIBILITY CRITERIA form [**EC. EC_IC_4**] = “Yes” OR “Not applicable: ICF waiver/Opt-out/No opposition applies”, AND
- “4. Informed and privacy consent signature obtained depending on local regulations” in the PROTOCOL DEVIATION FORM [**PDF. PDF_IC4**] is not flagged AND
- “Date of data collection (dd/mmm/yyyy)” [**PI. PI_date_coll**] is not missing.

Moreover, for patients with “4. Informed and privacy consent signature obtained depending on local regulations” in the ELIGIBILITY CRITERIA form [**EC. EC_IC_4**] = “Yes, it will be also verified that:

- “Date of informed consent form signature by the patient or by next of kin* (dd/mmm/yyyy)” [**PI. PI_date_IC**] <= “Date of data collection (dd/mmm/yyyy)” [**PI. PI_date_coll**] AND
- “Date of privacy form signature by the patient or by next of kin* (dd/mmm/yyyy)” [**PI. PI_date_priv**] <= “Date of data collection (dd/mmm/yyyy)” [**PI. PI_date_coll**]

During data elaboration this criterion will be critically reviewed and discussed, depending also on specificities of sites and countries local regulations.

Criterion 5 (UNCOMMON MUTATION COHORT). Patient harbouring uncommon or compound EGFR mutations

- “Cohort” [**PI. PI_coh_ty**] = “Uncommon Mutation cohort” AND
- “5. Patient harbouring uncommon or compound EGFR mutations” in the ELIGIBILITY CRITERIA form [**EC. EC_IC_5umc**] = “Yes” AND
- “5. Patient harbouring uncommon or compound EGFR mutations” in the PROTOCOL DEVIATION FORM [**PDF. PDF_IC5_umc**] is not flagged AND
- At least one uncommon mutation shall be present on the start date of the Index EGFR-TKI therapy (as defined in “Chapter 3”), according to the fields:
 - “EGFR mutations at start of first-line treatment” [**First-line treatment period / MUT1. MUT1_unc**]
OR
 - “EGFR mutations at start of second-line treatment” in the MUTATIONS form of the [**Second-line treatment period / MUT2. MUT2_mut_start**]

Criterion 5 (SEQUENCING COHORT). Patient with common EGFR mutations (Del19, L858R)

- “Cohort” [**PI. PI_coh_ty**] = “Sequencing cohort” AND
- “5. Patient with common EGFR mutations (Del19, L858R)” in the ELIGIBILITY CRITERIA form [**EC. EC_IC_5sc**] = “Yes” AND
- “5. Patient with common EGFR mutations (Del19, L858R)” in the PROTOCOL DEVIATION FORM [**PDF. PDF_IC5_sc**] is not flagged AND

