- from the OSIMERTINIB ADMINISTRATION DETAILS form (only for the SEQUENCING COHORT), from the field [OAD. OAD_dose] of the record with earliest non-missing start date (recorded in field [OAD. OAD_start_date]);
- from the EGFR-TKI ADMINISTRATION DETAILS form (only for the UNCOMMON MUTATION COHORT), from the field [EAD. EAD_dose] of the record with earliest non-missing start date (recorded field [EAD. EAD_start_date]). The same patient could have one or two lines of EGFR-TKI recorded in this form, and each line is identified by the field "Type of EGFR-TKI" [EAD. EAD_EGFR]: therefore, for each line recorded in this form, it will be possible to identify the starting dose with the rule defined above.

Index EGFR-TKI therapy

- *Uncommon mutation cohort*: it will correspond to the therapy recorded in the NSCLC TREATMENT form, either at [First-line treatment period] or [Second-line treatment period] depending on the following conditions:
 - [First-line treatment period] is the time point to consider if:
 - “Type of treatment” [First-line treatment period / TREAT. TREAT_ty] = “EGFR-TKI” AND
 - “Start date of this line (dd/mmm/yyyy)” [First-line treatment period / TREAT. TREAT_start_date] is lower than or equal to (“Date of data collection (dd/mmm/yyyy)” [PI. PI_date_coll] – 11.50 months) AND
 - “EGFR mutations at start of first-line treatment” [First-line treatment period / MUT1. MUT1_unc] has at least one of the options selected (excluding “Del19” and “L858R”) (*)
 - Otherwise, if the above-specified condition is not met, then the [Second-line treatment period] is the time point to consider if:
 - “Type of treatment” [Second-line treatment period / TREAT. TREAT_ty] = “EGFR-TKI” AND
 - “Start date of this line (dd/mmm/yyyy)” [Second-line treatment period / TREAT. TREAT_start_date] is lower than or equal to (“Date of data collection (dd/mmm/yyyy)” [PI. PI_date_coll] – 11.50 months) AND
 - “EGFR mutations at start of first-line treatment” [First-line treatment period / MUT1. MUT1_unc] OR “EGFR mutations at start of second-line treatment” in the MUTATIONS form of the [Second-line treatment period / MUT2. MUT2_mut_start] has at least one of the options selected (excluding “Del19” and “L858R”) (*)

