- **Major uncommon mutations:** patients having either G719X and/or L861Q and/or S768I mutations at start of either first- or second-line EGFR-TKI, excluding patients included in groups "a)" or "b");
- **Others:** patients not included in groups "a)", "b)", or "c");
- **Compound mutations:** patients having more than one mutation of any type (including also common mutations).

The same patient cannot be included in more than one of the following groups, which are mutually exclusive: a), b), c), d). On the contrary, the same patient can be included in group e) and also in another group a) or b) or c) or d).

Source: Chih-Hsin Yang J, Schuler M, Popat S, Miura S, Heeke S, Park K, Märten A, Kim ES, Afatinib for the Treatment of Non-Small Cell Lung Cancer Harboring Uncommon EGFR Mutations: A Database of 693 Cases, *Journal of Thoracic Oncology* (2020), doi: <https://doi.org/10.1016/j.jtho.2019.12.126>.

Classification of EGFR uncommon mutations at first-line treatment start

The same 5 classes described above will be considered, but considering only EGFR mutational status at first-line treatment start (see algorithm described before), and without restrictions on type of treatment line.

Classification of EGFR uncommon mutations at second-line treatment start

The same 5 classes described above will be considered, but considering only EGFR mutational status at second-line treatment start (see algorithm described before), and without restrictions on type of treatment line.

In particular, "T790M-positive" group includes also patients developing acquired T790M at second-line osimertinib start, while excludes patients with T790M acquired only and treated with osimertinib. However, if the patient had also additional acquired mutations at start of second-line osimertinib (and not only acquired T790M), then the patient will not be excluded.

Only patients with Number of NSCLC treatment lines (as defined before) > 1 and [**MUT2. MUT2_reeval**] = "Yes" will be considered.

Patients without mutations at second line treatment start will not be included in "Others".

Classification of EGFR uncommon mutations at second-line treatment stop/end of observation

The same 5 classes described above will be considered, but considering only EGFR mutational status at second-line treatment stop/end of observation (see algorithm described before), and without restrictions on type of treatment line.

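### In the SAP's exploratory mutation classification, a known first-line mutation is not used when the first line was not an EGFR-TKI and second-line status is Unknown, so the patient falls into Others

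*SAP*

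**What the plan says.** All rules below are for the uncommon mutation cohort. Unless stated otherwise they are in SAP chapter 3 (Computed variables).

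- **Eligibility (SAP 2.1, Criterion 5).** "At least one uncommon mutation shall be present on the start date of the Index EGFR-TKI therapy", shown by either the first-line field (MUT1) or the second-line field (MUT2).
- **Index EGFR-TKI therapy.** A second-line EGFR-TKI qualifies as index if the first-line field or the second-line field "has at least one of the options selected (excluding “Del19” and “L858R" apart. A first-line result alone is enough.
- **EGFR mutational status at second-line treatment start.** If there was no re-test, or the change is recorded as UNK, "patients will be classified as “Unknown EGFR mutational status". Only when the change field is No is the first-line result carried over: "EGFR mutational status at second-line treatment start will be imputed as the same patient’s EGFR mutational status at first-line treatment start".
- **Classification for exploratory analyses.** Classes are built by "considering the EGFR mutational status at first- and second-line treatment start (but considering only lines containing EGFR-TKIs". Groups a) T790M-positive, b) exon 20 insertion and c) major uncommon each need the mutation at the start of a first- or second-line EGFR-TKI. Group d), Others, is whoever is left over. Group e), compound, is a flag that can accompany any of the four. There is no Unknown class.
- **Classification at second-line treatment start.** This separate variable is limited to re-tested patients and has its own guard: "Patients without mutations at second line treatment start will not be included in" Others.
- **Missing data (SAP chapter 4).** Missing values are not imputed, and patients who lack a variable are left out of its analysis.

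**The concern.** One first-line test result is treated in two ways. For eligibility and for choosing the index line, it proves that the uncommon mutation was present when the index TKI started. For the exploratory classes it is set aside if the first line was not a TKI, and nothing replaces it if there was no usable re-test. A patient admitted because of G719X would then be filed as having none of the named mutations.

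The treatment path is one the SAP expects: its example sequences include chemotherapy with radiotherapy followed by erlotinib. Protocol 7.1 gives the benefit of individual TKIs in individual mutations as the reason for this cohort, and Protocol 9.5 projects numbers by mutation class. If Others absorbs known major, exon 20 or T790M cases, any result reported by these classes describes mixed groups. The patients lost from a) to c) would all be second-line-index patients.

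**Working it through.** **Step 1: follow the rules literally.** Take first-line chemotherapy, then a second-line EGFR-TKI started early enough to qualify, with the first-line mutation on record. Each such patient is eligible and has a second-line index.

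| First-line result | Class implied by that result | Exploratory class if not re-tested, or change UNK |
|---|---|---|
| G719X | Major | Others |
| Exon 20 insertion | Exon 20 | Others |
| T790M + L858R | T790M-positive, compound | Others, no compound flag |
| G719X + S768I | Major, compound | Others, no compound flag |
| E709X | Others | Others (correct) |

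The lost compound flag assumes that the TKI-line restriction in the lead-in also governs group e).

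Two controls locate the fault. With a re-test showing no change, all five patients get the right class. With a TKI as first line, all five get the right class whatever the re-test state. The fault needs both a non-TKI first line and an Unknown second-line status.

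**Step 2: check the neighbouring classifications.** The first-line-start classification uses the first-line result whatever the treatment type, so it places all five correctly; Table 9-UNC reports it. The second-line-start classification covers only re-tested patients and keeps those without mutations out of Others.

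**Step 3: size.** The plan states no figure for this group, so there is nothing to reproduce.

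Inputs from Protocol 9.5:
- About 250 patients.
- Historical shares of 46% major, 29% exon 20, 12% de novo T790M and 10% other.
- At least 50% with a first-line TKI, so at most 125 with a non-TKI first line.

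Assumptions, not in the documents:
- s, the share of the cohort with a second-line index TKI after a non-TKI first line: 10% to 50%, the upper end being the protocol's ceiling.
- r, the share of those with Unknown second-line status: 25% to 100%.
- The historical mutation mix applies to this group.

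Patients with Unknown status = 250 × s × r. Patients moved into Others = 250 × s × r × 0.87, where 0.87 = 0.46 + 0.29 + 0.12.

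| s | r = 25% | r = 50% | r = 100% |
|---|---|---|---|
| 10% | 5 | 11 | 22 |
| 25% | 14 | 27 | 54 |
| 50% | 27 | 54 | 109 |

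At s = 25% and r = 50%, 31.25 patients have Unknown status and about 27 move. Others grows from 25 (10% of 250) to about 52. Major loses 0.46 × 31.25 ≈ 14 of 115, and exon 20 loses 0.29 × 31.25 ≈ 9 of 72.5.

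These are rough figures. The five shares listed in Protocol 9.5 (the four above plus 13% complex or compound) sum to 110%, so categories overlap. If the whole 10-point excess were overlap among a) to c), the multiplier would be 0.77 and the range about 5 (6.25 × 0.77) to 96 (125 × 0.77).

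**The case against.** **It is only exploratory.** This stands as a limit on scope. A reader might infer that the SAP's mutation classification as a whole is wrong, or that the main results are affected. The documents do not support either. Tables 36-, 37- and 38-UNC and the response tables run on eligible patients, or on those with more than one line, without these classes. Table 37-UNC excludes T790M acquired only at second-line osimertinib start, but that is not a use of the classes. No stated objective is defined by mutation class, and the protocol's checklist (Annex 2, item 10.4) says no stratified analysis is planned.

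**Class results may not be distorted.** A reader might go on to conclude that results by class will be confounded with line of therapy. That cannot be confirmed. Tables 39- to 48-UNC appear only in the SAP revision history, and the visible text does not show which tables use this variable. They may be split by line or handle Unknown separately.

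**Others is not the only reading.** Under the chapter 4 missing-data rule, Unknown patients would be excluded rather than misfiled. A programmer following Criterion 5 might also treat the first-line mutation as present at index start and classify correctly. Group e) has no start-of-TKI wording of its own, so loss of the compound flag is less certain. These points show that the outcome depends on the reader; they do not remove the gap. The SAP's own definition makes second-line status Unknown, which favours the literal result, and exclusion would still discard a recorded mutation.

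**The size is assumed.** This stands. The range mostly reflects the chosen s and r.

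**Conclusion.** The concern holds for one derivation, the classification for exploratory analyses. For a non-TKI first line, a second-line index TKI and no usable re-test, the literal rules put a known major, exon 20 or de novo T790M mutation into Others and may drop the compound flag. Read through the missing-data rule, they drop a patient whose mutation is recorded. Both outcomes conflict with the eligibility and index rules, which rely on that same first-line result.

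The first-line-start and second-line-start classifications and the visible primary and secondary tables are not affected. The number of patients is unknown; under the stated assumptions it runs from about 5 to about 109 of 250. No single figure in that range should be quoted as expected.

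**What to change.** Confine the change to the exploratory classification in SAP chapter 3:

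1. State that when second-line status is Unknown and the first line was not an EGFR-TKI, the first-line (MUT1) status is used for groups a) to e), including the compound flag.
2. Define Others as at least one known uncommon mutation that is not in a) to c), in place of the residual definition.
3. Report how many patients are classified on a carried-forward result.

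With item 1, every test patient above returns to the class implied by the first-line result, and E709X stays in Others.

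Two broader edits should be avoided. Changing the definition of second-line mutational status would make untested patients appear as known in Table 12-UNC, so that definition and the table's Unknown row should stay as they are. Deleting the TKI-line restriction outright would let a superseded first-line result override an actual re-test.

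The cost is a few sentences of SAP text and one programming change; the data are already in the eCRF. The downside is small: an untested mutation change during the non-TKI first line is assumed absent, and the count in item 3 shows how many patients rest on that assumption.
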